2.0	April 27, 2016	Add Section 4.2.1.2 Blinded Sample Size Re Estimation
2.0	April 27, 2016	Add Appendix A – Sample Size Calculation with PASS
2.0	April 27, 2016	Sec 4.4.4 Safety Analysis – Remove “Application to target area”.
2.0	April 27, 2016	Sec 4.4.4 Safety Analysis - Delete “Potentiation” Add “Exacerbation”
2.0	April 27, 2016	Sec 4.6 Covariate Analysis – Add “Complement C3”
2.0	April 27, 2016	Add Appendix B Blinded Sample Size Re estimation Simulation

[figure not shown]
Version Number	Effective Date	Detail of Changes
2.0	April 27, 2016	Sec 4.7 Modification of alpha to 0.15
2.0	April 27, 2016	Add new References
3.0	June 15, 2016	Sec 4.2.1.2 Add “minimum planned enrollment of 324”
3.0	June 15, 2016	Sec 4.2.1.2 Add “which may be lower or higher than the re-estimated sample size after 20% enrollment”
3.0	June 15, 2016	Sec 4.2.1.2 Add “The loss rate due to technical failures at the interim analysis will be estimated and provided to the DSMB. In making a sample size recommendation, the DSMB may adjust the re-estimated sample size by up to 5% for the loss rate.”
3.0	June 15, 2016	Sec 4.2.1.2 Add “ Max sample size is at “536(510 with a 5% loss adjustment)”
3.0	June 15, 2016	Sec 4.2.1.2 Modification of Blind Sample Size Re-Estimation
3.0	June 15, 2016	Sec 4.2.1.2 Update Table 1 Title : “Re-estimated Sample Size based on blind efficacy rate before adjusting for loss”
3.0	June 15, 2016	Sec 4.2.1.2 Update Table 1 header “Sample Size” to “Sample Size Re-estimation”
3.0	June 15, 2016	Sec 4.2.1.2 Update Table 1 Sample Size Re-estimation values.
3.0	June 15, 2016	Sec 4.2.1.2 Add “before adjusting for loss”
3.0	June 15, 2016	Sec 4.2.1.2 Update Table 2 Fixed Sample size and Blind Sample Size re-estimation values.
3.0	June 15, 2016	Sec 4.2.1.2 Add “DSMB recommends that....at an interim analysis”
3.0	June 15, 2016	Sec 4.2.1.2 Remove “at the time the study is stopped”
3.0	June 15, 2016	Sec 4.2.1.2 Add “statistical criteria for rejecting the null hypothesis will”
3.0	June 15, 2016	Sec 4.2.1.2 Add “data may not be sufficientdiscussion with the FDA is warranted prior to closure of the trial”
3.0	June 15, 2016	Sec 4.2.1.2 Add “regardless of the observed efficacy and loss rates”
3.0	June 15, 2016	Sec 4.2.1.2 Remove “due to technical failures”
3.0	June 15, 2016	Sec 4.6 Covariate Analysis deleted “Acid Base Status”
3.0	June 15, 2016	Sec 2 Study Subjects Add “ For oncology subjects, an additional follow-up will occur at 24 months”

10 JULY 2018
Date

Table of Contents

1	Study Design and Objectives.....	1
2	Study Subjects	2
3	Randomization and Blinding	2
4	Statistical Methods.....	3
4.1	Study Objectives	3
4.2	Study Hypotheses.....	3
4.2.1	Primary Efficacy	3
4.2.1.1	Sample Size Justification	4
4.2.1.2	Blinded Sample Size Re-estimation.....	4
4.2.2	Secondary Efficacy	7
4.2.3	Trial Success Criteria.....	7
4.3	Analysis Populations.....	7
4.4	Analysis Methods.....	8
4.4.1	General Statistical Considerations	8
4.4.2	Primary Efficacy	8
4.4.3	Secondary Efficacy	10
4.4.4	Safety Analyses.....	10
4.5	Subgroup Analysis.....	12
4.6	Covariate Analysis.....	12
4.7	Poolability Analysis.....	13
4.8	Missing Data	14
5	Analysis Software.....	14
Appendix A – Sample Size Calculation with PASS		15
Appendix B – Blinded Sample Size Re-estimation Simulation.....		17
References		21

1 Study Design and Objectives

The device under investigation is PerClot® Polysaccharide Hemostatic System (hereinafter referred to as PerClot). This is a prospective, multicenter, multidisciplinary, controlled clinical investigation evaluating the safety and efficacy of PerClot compared to a similar marketed hemostatic device.

The overall objective of this clinical investigation is to collect clinical data concerning the safety and efficacy of PerClot versus a similar marketed hemostatic device (the control) in multiple surgical disciplines when used as an adjunct to conventional means of achieving hemostasis such as pressure or ligature. Hemostasis is defined as complete cessation of bleeding.

The primary endpoint of this investigation is to demonstrate non-inferiority in the achievement of hemostasis of the treated bleeding site at 7 minutes in subjects receiving PerClot compared to subjects receiving a control hemostatic device. The secondary objective of this investigation is to compare the achievement of hemostasis of the treated bleeding site at 5 minutes in subjects receiving PerClot compared to subjects receiving a control hemostatic device.

The primary endpoint measure is hemostasis of the treated bleeding site at 7 minutes. The secondary efficacy endpoint measure for this investigation is hemostasis of the treated bleeding site at 5 minutes.

Safety data will be summarized by incidence of each adverse event type. Adverse events will be summarized by relatedness, seriousness, and severity. Additional safety endpoints will also consist of:

- Total operative time;
- Hemostasis at 5 and 7 minutes;
- Hemostasis maintenance;
- Total intraoperative estimated blood loss;
- Alternative means required to achieve hemostasis (where applicable);
- Units of blood transfused intraoperatively and postoperatively (where applicable);
- Incidence of reoperation;
- Total hospitalization time;
- The incidence of procedure complications; and
- The incidence of adverse events through final follow-up, including, but not limited to:
 - Adhesions or fibrosis;
 - Anaphylaxis;
 - Blockage of the bladder or ureteral lumen;
 - Blockage of the bypass system;
 - Cancer recurrence and/or progression;
 - Compromised attachment of prosthetic devices to bone or tissue;
 - Death;
 - Embolism;
 - Failure of deep or superficial wound healing;
 - Failure to obtain hemostasis;
 - Fever;

- Hemorrhage;
- Infection;
- Peri-operative hyperglycemia;
- Exacerbation of surgical procedure-associated adverse events;
- Swelling and compression of pressure-sensitive tissues and structures;
- Thromboembolism;
- Thrombosis; and
- Toxicity.

Any procedure complications/adverse events through final follow-up will be reported as per Common Terminology Criteria for Adverse Events (2009): CTCAE-2009.¹

2 Study Subjects

Three hundred and twenty four subjects across a maximum of 25 investigational sites undergoing open elective cardiac, general, or urological surgical procedures who meet the eligibility criteria will be intraoperatively randomized to receive either PerClot or the control hemostatic device. Subjects will be randomized on a 1:1 basis. Randomization will be stratified by therapeutic area and bleeding severity score within site. Each investigational site is expected to enroll approximately 13-40 subjects. All investigational sites will be located in the U.S. Follow-up will occur at hospital discharge and 6 weeks post-device application.

The expected duration of each subject's participation in this investigation can range from a minimum of 28 to 56 days, based on the visit windows presented in Table 1. For oncology subjects, an additional follow-up will occur at 24 months.

Table 1: Visit Windows for Evaluations

Visit Type	Timing
Preoperative	Within 1 month (30 days) before operative visit
Operative	Day 0
Postoperative	Within 24 hours postoperatively
Follow-Up: Discharge	Within 24 hours of hospital discharge or between 24 hours and 14 days postoperatively
Follow-Up: 6 weeks	28 - 56 days postoperatively
Follow-Up: 24 Months*	23-25 months (700-760 days) postoperatively

*For oncology subjects only.

3 Randomization and Blinding

The randomization schedule will be stratified by site, therapeutic area, and bleeding severity score, and will be generated using random permuted blocks of size two and four. Subjects will be randomized on a 1:1 allocation to either PerClot or the control group. A subject may agree to participate and sign the ICF, but ultimately not be enrolled due to failure to meet the intraoperative eligibility criteria. Only subjects meeting the intraoperative eligibility criteria will be randomized and enrolled.

This will be a single-blinded trial. The subjects will be blinded as to the hemostatic treatment received. Unblinding will be permitted after a subject has completed his or her 6 week follow-up visit evaluations.

4 Statistical Methods

4.1 Study Objectives

The primary objective of this clinical investigation is to demonstrate non-inferiority in the achievement of hemostasis of the treated bleeding site at 7 minutes in subjects receiving PerClot compared to those receiving a control hemostatic device.

The secondary objective of this investigation is to compare the achievement of hemostasis of the treated bleeding site evaluated at 5 minutes for subjects receiving PerClot compared to those receiving a control hemostatic device.

4.2 Study Hypotheses

4.2.1 Primary Efficacy

The primary efficacy hypothesis for this clinical investigation is that the proportion of subjects achieving hemostasis of the treated bleeding site at 7 minutes in the PerClot group is non-inferior to the proportion of subjects achieving hemostasis at 7 minutes in the control group.

$$H_0: P_{\text{PerClot}} < P_{\text{Control}} - \delta$$

$$H_a: P_{\text{PerClot}} \geq P_{\text{Control}} - \delta$$

where P_{PerClot} is the proportion of PerClot subjects achieving hemostasis at 7 minutes, P_{Control} is the proportion of control subjects achieving hemostasis of the treated bleeding site at 7 minutes, and δ is the non-inferiority margin, with $\delta = 0.10$.

In other words, the null hypothesis is that the proportion of PerClot subjects achieving hemostasis of the treated bleeding site at 7 minutes will be inferior to the proportion of control subjects achieving hemostasis of the treated bleeding site at 7 minutes. The alternative hypothesis is that the proportion of PerClot subjects achieving hemostasis of the treated bleeding site at 7 minutes will be equal to or greater than, or not inferior to, the proportion of control subjects achieving hemostasis of the treated bleeding site at 7 minutes. The null hypothesis will be rejected in favor of the alternative hypothesis if the upper bound of the 97.5% one-sided confidence interval for the difference in treatment proportions ($P_{\text{Control}} - P_{\text{PerClot}}$) is less than 0.10.

4.2.1.1 Sample Size Justification

The sample size was calculated based on the following assumptions:

- One-sided alpha = 0.025;
- Minimum 80% power;
- Non-inferiority margin $\delta = 0.10$;
- Expected 7 minute hemostatic success rate in the PerClot group is 90%; and
- Expected 7 minute hemostatic success rate in the control group is 90%.
- Randomization allocation of 1:1

A sample size of 154 subjects in each group will provide approximately 80% power to reject the hypothesis of the inferiority of PerClot to the composite control by a 10% margin, using a one-sided 97.5% confidence interval (see Appendix A). As the primary endpoint data is collected intraoperatively, no adjustment is made for attrition; however, the sample size was increased to account for the possibility of up to 5% loss within either group due to technical failures (i.e., contraindications, misdiagnosis, or intraoperative death prior to treatment, etc.), and subjects not treated according to randomization assignment, resulting in a sample size of 162 per arm to ensure >80% power. Thus, a total of 324 subjects is the planned sample size to enroll, assuming an efficacy rate of 90%.

A non-inferiority margin of 10% is consistent with the margins used in other controlled clinical trials involving hemostatic agents.^{2, 3} A non-inferiority margin $\delta = 0.10$ was chosen for this study because excluding a 10% difference between the treatments would be supportive of non-inferior performance of PerClot compared to the control.

4.2.1.2 Blinded Sample Size Re-estimation

In order to protect against lower than planned power due to misspecification of the assumed success rates, blinded sample size re-estimation (BSSR) will be performed⁴. The initial sample size calculation will be repeated based on the observed pooled efficacy rate (i.e. the proportion of all subjects, regardless of randomization assignment, with 7 minute hemostatic success) rather than the initially assumed rate of 90%.

The re-estimation will be performed using the pooled efficacy results of the first 20% and 50% of the minimum planned enrollment of 324 (i.e. 64 and 162 subjects). The re-estimated sample size after 20% enrollment will provide an initial re-calibration of the sample size. The re-estimated sample size after 50% enrollment will determine the final sample size, which may

be lower or higher than the re-estimated sample size after 20% enrollment.

The sample size calculation will result in an increase in sample size if the observed efficacy rate is less than 90%. The loss rate at the interim analysis will be estimated and provided to the DSMB. In making a sample size recommendation, the DSMB may adjust the re-estimated sample size by up to 5% for the loss rate. The minimum sample size for the trial, regardless of the observed efficacy and loss rates, is the initially planned sample size of 324. A maximum sample size is set at 536 (510 with a 5% loss adjustment) for any observed efficacy rate $\leq 80\%$. The table below provides examples of the revised sample size before adjusting for loss based on hypothetical results.

Table 2: Re-estimated sample size based on blinded efficacy rate before adjusting for loss

Blinded Efficacy Rate	Re-estimated Sample Size
90%	308
89%	332
88%	352
87%	374
86%	394
85%	414
84%	434
83%	454
82%	474
81%	492
80%	510

Because the sample size re-estimation is blinded and based only on a nuisance parameter, there is no impact on the Type I error rate. Larger sample sizes are required due solely to greater variability in the binomial outcome when the equal PerClot and control efficacy rates are closer to 50%, at which point variability is at a maximum.

The Type I error, average sample size before adjusting for loss, and power were evaluated through a statistical simulation where binomial data was generated under several alternative hypotheses where the efficacy rate is equal between the two arms, but the efficacy rate is varied from 70% through 90%. The simulation results in the table below demonstrate that the Type I error is not inflated when the sample size is increased based on the pooled efficacy estimate and that power is maintained at 80% across all scenarios. The R code for the simulation is provided in Appendix B.

Table 3: Fixed versus BSSR Power and Sample Size Under Various Alternative Hypotheses

Alternative hypotheses (equal success rates)	Fixed Sample Size		Blinded Sample Size Reestimation (after 20% and 50% of subjects)	
	Sample Size (total after 5% loss)	Simulated Power	Final Sample Size (mean total after 5% loss)	Simulated Power
90%	308	81.1%	328	83.9%
85%	308	68.2%	414	80.1%
80%	308	59.0%	486	78.6%
75%	308	52.8%	508	73.9%
70%	308	48.3%	510	69.2%
Null hypothesis	Sample Size (total after 5% loss)	Type I Error	Final Sample Size (mean total after 5% loss)	Type I Error
80% (PerClot) vs 90% (Control)	308	2.3%	414	2.4%

If the observed efficacy rate is $\leq 60\%$ when the blinded sample size re-estimation is performed at 20% of enrollments or $\leq 64\%$ when the blinded sample size re-estimation is performed at 50% of enrollments, the DSMB will evaluate the overall study data and make a recommendation regarding whether to stop the study prematurely due to an unacceptable efficacy rate. The boundaries of 60% and 64% were selected based on those observed rates have $<5\%$ chance of being observed if the population efficacy rate is 70% or higher.

In the event that the DSMB recommends that the study be stopped due to low efficacy at an interim analysis, the two study arms will be compared based on the available data in the As Treated population. There is the possibility that a low pooled success rate is due primarily to one of the two study arms. If the PerClot success rate is sufficiently higher than the control success rate that the non-inferiority Z-value would cross a group sequential boundary based on a Lan-DeMets alpha-spending function with the information fraction based on the planned sample size of 324 (boundaries are $Z=4.42$ at 20% and $Z=2.80$ at 50%), then the statistical criteria for rejecting the null hypothesis will be met based on the available data. However, as the data may not be sufficient to adequately assess the overall performance of PerClot in this scenario, discussion with FDA is warranted prior to closure of the trial.

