# Re-estimated Sample Size Table
# original sample size of 154 per arm based on approximately 80% power
# efficacy rate of 0.901 used to match sample size of 154 per arm after 5% loss
effrates <- c(0.901, 0.89, 0.88, 0.87, 0.86, 0.85, 0.84, 0.83, 0.82, 0.81, 0.80)
cbind(round(effrates, 2), sapply(effrates, function(x) { 2*ssFMnoninf(pA=x, pB=x)}))

ssFMnoninfeq <- function(pooled.estimate, tol=10**-3)
{

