# Type 1 Error
binarynoninfsim(n.sim=10**5, n.init=154, n.interim1max=154, n.interim2max=255,
prop.interim1=0.2, prop.interim2=0.5,

```

pA=0.8-10**-3, pB=0.9, margin=-0.1, alphaBSS=0.025, alphaFIX=0.025)

```

effrates <- c(0.901, 0.85, 0.80, 0.75, 0.70)
interim.n.equal <- sapply(effrates, function(a) { binarynoninfsim(n.sim=10**5,
n.init=154, n.interim1max=154, n.interim2max=255,
prop.interim1=0.2, prop.interim2=0.5,
pA=a, pB=a, margin=-0.1,
alphaBSS=0.025, alphaFIX=0.025) })
interim.n.equal

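### The SAP says blinded re-estimation holds power at 80% in every simulated scenario, but its own Table 3 shows 78.6%, 73.9% and 69.2% at success rates of 80%, 75% and 70%

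*SAP*

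**What the plan says.** SAP 4.2.1.1 sets the design targets: "One-sided alpha = 0.025", "Minimum 80% power", a margin of 0.10, 90% expected success in each arm and 1:1 allocation. This gives 154 per arm, or 308 evaluable subjects.

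SAP 4.2.1.2 adds a blinded re-estimation whose stated purpose is to guard against power falling below plan if the assumed success rates are wrong. The total is recalculated from the pooled success rate, subject to a ceiling: "A maximum sample size is set at 536 (510 with a 5% loss adjustment) for any observed efficacy rate" of 80% or lower. The simulation takes equal success rates in the two arms, from 70% to 90%. The text says it shows no inflation of the Type I error "and that power is maintained at 80% across all scenarios".

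Table 3 then gives:

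| Common success rate | Mean final N (after loss) | Power with re-estimation |
|---|---|---|
| 90% | 328 | 83.9% |
| 85% | 414 | 80.1% |
| 80% | 486 | 78.6% |
| 75% | 508 | 73.9% |
| 70% | 510 | 69.2% |

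Appendix B contains the simulation code. A comment beside the calculation of the re-estimated sample sizes reads "efficacy rate of 0.901 used to match sample size of 154 per arm after 5% loss". The Type I error run sets the PerClot rate at 0.8 minus 0.001, against 0.9 for control.

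**The concern.** Three of the five scenarios are below 80%, so the sentence and the table cannot both be right. Nothing in the SAP or protocol restricts the sentence to the higher success rates.

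The sentence is the SAP's own verdict on whether the re-estimation does its job, so the error matters. The low rates are also ones at which the trial would normally carry on. The DSMB low-efficacy review is triggered at a pooled rate of 60% or lower at the first look and 64% or lower at the second. Those thresholds were chosen to have less than a 5% chance of being met when the true rate is 70% or more. With a true rate of 70% to 80% the trial would usually continue, with the cap in force in many or most cases. A DSMB advising on sample size, or a regulator, who relied on the sentence would think 80% power was secured there. At 70% a device exactly as good as the control would fail non-inferiority about 3 times in 10.

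**Working it through.** **Inputs.** One-sided alpha 0.025 (z = 1.960), target power 80% (z = 0.842), margin 0.10 and 1:1 allocation come from SAP 4.2.1.1. The Farrington-Manning score test comes from Appendix A. The minimum of 154 and maximum of 255 per arm come from the Appendix B calls. Because the code holds the first-look total at 154 per arm, the second look is always at 77 per arm and it alone sets the final size.

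**Formula.** For a common success rate p:

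- n per arm = (1.960·s0 + 0.842·s1)² / 0.10²
- power at n per arm = Φ[(0.10·√n − 1.960·s0) / s1]

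Here s1 = √[2p(1−p)] and s0 = √[p̃1(1−p̃1) + p̃2(1−p̃2)], where p̃1 and p̃2 are the success rates fitted under the restriction p̃1 − p̃2 = −0.10.

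**Reproducing the plan's figures.** At p = 0.90, p̃1 = 0.8313 and p̃2 = 0.9313, so s0 = 0.4519 and s1 = 0.4243. With n = 154, power = Φ[(1.2410 − 0.8857)/0.4243] = Φ(0.837) = 0.799. Appendix A has 0.79885. The formula also returns every total in SAP Table 2 from 89% (332) down to 80% (510). For the 90% row it returns 308 only at p = 0.901 (153.3, rounded up to 154 per arm). At exactly 0.90 it needs 154.4, hence 155 per arm and 310 in total.

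**Sample size needed for 80% power.**

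| p | s0 | s1 | n per arm | Total | Cap |
|---|---|---|---|---|---|
| 0.85 | 0.5171 | 0.5050 | 206.9 → 207 | 414 | 510 |
| 0.80 | 0.5706 | 0.5657 | 254.2 → 255 | 510 | 510 |
| 0.75 | 0.6135 | 0.6124 | 295.1 → 296 | 592 | 510 |
| 0.70 | 0.6471 | 0.6481 | 328.9 → 329 | 658 | 510 |

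Even if every trial ran to the cap (255 per arm), power would be Φ[(1.5969 − 1.2024)/0.6124] = 74.0% at 75% and Φ[(1.5969 − 1.2683)/0.6481] = 69.4% at 70%. At 80% the required total equals the cap. A chance high pooled rate at the look lowers N, and a chance low one cannot raise it. The mean N is therefore 486 and power falls just short.

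**Power of the whole rule.** All interim and final binomial outcomes were enumerated exactly: pooled rate at 77 per arm, final n between 154 and 255 per arm, final score test. A separate simulation used 400,000 trials per scenario. Its 90% row was run at 0.901, as in the SAP code; the enumeration was run at 0.90.

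| Rate | SAP Table 3 | Exact | Simulation | Trials at the cap |
|---|---|---|---|---|
| 90% | 83.9% | 83.7% | 83.8% | about 0% |
| 85% | 80.1% | 80.3% | 80.2% | 5% |
| 80% | 78.6% | 78.4% | 78.5% | 52% |
| 75% | 73.9% | 74.1% | 74.1% | 93% |
| 70% | 69.2% | 69.5% | 69.6% | 99.8% |

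Against 80%, Table 3 is short by 1.4, 6.1 and 10.8 points in the last three rows; the exact figures are short by 1.6, 5.9 and 10.5.

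**Is the cap the cause?** With the cap removed, simulated power is 80.0%, 80.0% and 79.9% at 80%, 75% and 70%, with mean totals of about 507, 588 and 655. With 536 evaluable subjects (no loss at all, 268 per arm) it is still 79.3%, 76.0% and 71.7%.

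**Type I error row.** Table 3 labels it 80% versus 90% and gives 2.4%. At the 0.799 versus 0.90 actually coded, the exact value is 2.35%. At 0.80 versus 0.90 it is 2.51%.

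**The case against.** Several points on the other side are fair.

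- The correct figures are printed directly beneath the sentence, and the cap is stated openly in the same section. A reader who checks the table is not misled. This tempers the consequence but does not make the sentence true.
- The 80% row is within 1.4 points of target and could pass as roughly 80%. That stands; the material shortfall is at 75% and 70%.
- A device as good as the control would fail 2 times in 10 even at the planned power, so the excess at 70% is about 1 in 10. That is at a rate 20 points below the planning assumption, where the fixed design would have only 48.3% power. The re-estimation clearly helps; it just does not deliver what the sentence says.
- The use of 0.901 is disclosed in Appendix B, and the 308 in Table 2 is the planned design, which Appendix A gives at exactly 0.90 with power 0.79885. The effect on Table 3 is about 0.2 points (83.9% against 83.7%).
- As the SAP writes its hypotheses, the null is a strict inequality, so 0.80 versus 0.90 formally belongs to the alternative and 0.799 is a legitimate null point. The boundary is still the more informative place to look, but 2.51% is essentially nominal and the statement that Type I error is not inflated survives.

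The last two points make the labelling matters minor. None of the five rescues the claim about all scenarios.

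**Conclusion.** The concern holds. Table 3 is correct and the sentence summarising it is wrong. Under the planned rule, power is about 80% or more at common success rates of 85% and 90%, marginally short at 80% (78.6%), and clearly short at 75% (73.9%) and 70% (69.2%). The cap of 510 evaluable subjects explains the shortfall. The result assumes equal true rates in the two arms, the score test and one-sided 0.025 level named in the SAP, and the decision rule as coded in Appendix B. It needs no outside figures. The Type I error half of the sentence is supported. The 90.1% and 79.9% inputs behind the rounded row labels are real discrepancies but change no conclusion.

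**What to change.** Replace the power clause in SAP 4.2.1.2 with wording such as: *Power is about 80% or more when the common success rate is 85% or higher. Because the sample size is capped at 510 evaluable subjects, simulated power is 78.6% at a rate of 80%, 73.9% at 75% and 69.2% at 70%.*

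Add a footnote to Tables 2 and 3 saying that the 90% rows were computed at 90.1% to match the planned 154 per arm (the formula gives 310 in total at exactly 90%). Rerun the Type I error row at exactly 0.80 versus 0.90, or state that it was run at 0.799.

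This costs a few lines of SAP text and one rerun of existing code. There are no extra patients and no change to margin, alpha, cap or success rule; the stated power simply becomes less favourable below 85%.

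If the sponsor does want 80% power at the lower rates, the cap itself would have to rise to 592 evaluable subjects for 75% (82 more than 510) or 658 for 70% (148 more). That is a design decision, and correcting the text does not require it.

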# n.interim1 is the expected effective sample size at the 1st interim, after 5% loss
n.interim1 <- round(n.init * prop.interim1)

a.interim1 <- rbinom(n=n.sim, size=n.interim1, prob=pA)
b.interim1 <- rbinom(n=n.sim, size=n.interim1, prob=pB)

pooled.estimate.interim1 <- (a.interim1 + b.interim1) / (2*n.interim1)
sample.sizes.interim1 <- ssFMnoninfseq(pooled.estimate.interim1, tol)
n.total.interim1 <- pmin(n.interim1max, pmax(n.init, sample.sizes.interim1))

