# n.interim2 is the expected effective sample size at the 2nd interim, after 5% loss
n.interim2 <- round(n.total.interim1 * prop.interim2)

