# when !interim2GEinit
# or simulate all n.tointerim2 at once
n.tointerim2[!interim2GEinit] <- n.interim2[!interim2GEinit] - n.interim1
a.interim2[!interim2GEinit] <- a.interim1[!interim2GEinit] +
rbinom(n=n.interim2LTinit, size=n.tointerim2[!interim2GEinit], prob=pA)
b.interim2[!interim2GEinit] <- b.interim1[!interim2GEinit] +
rbinom(n=n.interim2LTinit, size=n.tointerim2[!interim2GEinit], prob=pB)

pooled.estimate.interim2 <- (a.interim2 + b.interim2) / (2*n.interim2)
sample.sizes.interim2 <- ssFMnoninfeq(pooled.estimate.interim2, tol)
n.total.interim2 <- pmin(n.interim2max, pmax(n.total.interim1, sample.sizes.interim2))

prob.ss.10pct.interim2 <- sum(abs(n.total.interim2 - correct.ss)/correct.ss < 0.1)/n.sim
prob.ss.5pct.interim2 <- sum(abs(n.total.interim2 - correct.ss)/correct.ss < 0.05)/n.sim

n.tofinal <- n.total.interim2 - n.interim2

a.final <- a.interim2 + rbinom(n=n.sim, size=n.tofinal, prob=pA)
b.final <- b.interim2 + rbinom(n=n.sim, size=n.tofinal, prob=pB)

n.final <- n.total.interim2

pvals <- 1-pnorm(testBinomial(a.final, b.final, n.final, n.final, delta0=-0.1)) # one-sided
by default

n.tofix[!interim2GEinit] <- n.init - n.interim2[!interim2GEinit]
a.fix[!interim2GEinit] <- a.interim2[!interim2GEinit] + rbinom(n=n.interim2LTinit,
size=n.tofix[!interim2GEinit], prob=pA)
b.fix[!interim2GEinit] <- b.interim2[!interim2GEinit] + rbinom(n=n.interim2LTinit,
size=n.tofix[!interim2GEinit], prob=pB)
n.fix[!interim2GEinit] <- n.interim2[!interim2GEinit] + n.tofix[!interim2GEinit]

pvalsfix <- 1-pnorm(testBinomial(a.fix, b.fix, n.fix, n.fix, delta0=-0.1)) # one-sided by
default

return(list(n.interim1=n.interim1, n.interim2.mean=mean(n.interim2),
fix.power=sum(pvalsfix<alphaFIX)/n.sim,
bssr.power=sum(pvals<alphaBSS)/n.sim,
ss.mean=mean(n.final), ss.sd=sd(n.final),
ss.min=min(n.final), ss.max=max(n.final),
ss.probmax=sum(n.final==n.interim2max)/n.sim,
ss.wi10pct=prob.ss.10pct.interim2, ss.wi5pct=prob.ss.5pct.interim2))

}

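### Do the early-rejection bounds of 4.42 and 2.80 need correcting because the Lan-DeMets function behind them is not named?

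*SAP*

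**What the plan says.** SAP 4.2.1.2 schedules two blinded re-estimations of sample size, at 20% and 50% of 324 ("i.e. 64 and 162 subjects"). If pooled 7-minute success is at most 60% at the first or at most 64% at the second, the DSMB reviews the study and may recommend stopping. If it does, "the two study arms will be compared based on the available data in the As Treated population". The criterion for rejecting the null hypothesis is met if the Z-value "would cross a group sequential boundary based on a Lan-DeMets alpha-spending function" "with the information fraction based on the planned sample size of 324". The values are then printed: "boundaries are $Z=4.42$ at 20% and $Z=2.80$ at 50" per cent. The SAP adds that FDA should be consulted before the trial is closed.

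Neither document names a spending function or pairs a final critical value with these two bounds. SAP 4.2.3 and protocol 6.6.7 set the end-of-trial test as a one-sided 97.5% confidence bound, that is, Z = 1.96. Appendix B does not compute the interim bounds. Its rejection rate counts only the end-of-trial test ("bssr.power=sum(pvals<alphaBSS)/n.sim").

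**The concern.** Lan-DeMets is a framework. Until a function is chosen it fixes no boundary, so the label alone cannot be checked against the numbers. When the usual choices are tried, none gives both 4.42 and 2.80, whereas a different method, the classical O'Brien-Fleming boundary, gives both to two decimals. That looks like a wrong attribution in a rule for rejecting the primary null hypothesis on unblinded data.

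Two consequences would matter if they were real. If the bounds had to be recalculated at a different information fraction, an analyst would not know which function to use and might choose after unblinding. If the trial carried on after the comparison, a final test at 1.96 would take no account of the error already spent.

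**Working it through.** **Inputs.** One-sided alpha 0.025 (SAP 4.2.1.1); looks at 20%, 50% and 100% of 324, bounds 4.42 and 2.80, stopping triggers of 60% and 64%, and maximum size 536, or 510 after 5% loss (SAP 4.2.1.2); 154 per arm after loss (SAP 4.2.1.1 and Appendix B).

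**Method.** Under the null the Z-values at fractions t_j < t_k are standard normal with correlation sqrt(t_j/t_k). The error at each look is the probability of crossing there for the first time, found by recursive numerical integration.

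**1. Reproducing the printed pair.** Classical O'Brien-Fleming sets c_k = C/sqrt(t_k). A total of 0.025 at looks 0.2, 0.5 and 1 gives C = 1.9775. Then 1.9775/sqrt(0.2) = 4.422 and 1.9775/sqrt(0.5) = 2.797, with final value 1.977. Both printed values are matched. The match needs the nominal 20%; at 64/324 = 19.75% the first bound is 4.45.

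**2. Lan-DeMets functions at the same looks.**

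| Function | 20% | 50% |
|---|---|---|
| O'Brien-Fleming type, one-sided 0.025: 2[1 - Phi(2.2414/sqrt t)] | 4.88 | 2.96 |
| O'Brien-Fleming type, two-sided 0.05, per side: 1 - Phi(1.96/sqrt t) | 4.38 | 2.77 |
| Pocock type | 2.44 | 2.33 |
| Hwang-Shih-DeCani, -4 | 3.25 | 2.80 |
| Hwang-Shih-DeCani, -8 | 3.99 | 3.34 |
| Power family, rho = 3 | 3.54 | 2.75 |
| Power family, rho = 5 | 4.31 | 3.17 |

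At 64/324 the first two rows become 4.91/2.96 and 4.41/2.77. No row gives both values.

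**3. Are the printed bounds valid?** They spend 4.9e-6 at 20% and 0.00255 at 50%, in total 0.00256, or 0.26% of the 2.5% available. With the stopping triggers applied and the stop treated as final (32 and 81 per arm at the looks, 255 per arm at the end, Farrington-Manning Z, 2,000,000 runs), total one-sided error is:

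| Null rates, control / PerClot | 4.42/2.80 | 4.88/2.96 | 4.38/2.77 |
|---|---|---|---|
| 75% / 65% | 2.38% | 2.38% | 2.38% |
| 70% / 60% | 1.56% | 1.54% | 1.57% |
| 65% / 55% | 0.47% | 0.43% | 0.49% |

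All are below 2.5%, and the choice of bound shifts them by at most 0.04 percentage points.

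**4. What would another bound change?** Take 81 per arm and 102 successes in 162. With 56 on PerClot and 46 on control, the difference plus margin is 10/81 + 0.10 = 0.223 and Z = 2.95. This crosses 2.80 but not 2.96. One success moved from control to PerClot (57 and 45) gives 12/81 + 0.10 = 0.248; the standard error depends on the pooled count only very slightly, at about 0.223/2.95 = 0.0757, so Z is about 3.28 and crosses both. In the other direction, 56 and 47 gives Z = 2.7975, which crosses 2.77 but not 2.80. The printed bounds are stricter than one candidate and more lenient than the other, by about one subject per arm.

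**5. How often is the path opened?** At the 50% look the trigger is at most 103 of 162 (0.64 x 162 = 103.68). The binomial probability is about 2e-19 if true success is 90%, 9e-7 at 80% and 4.7% at 70%. A DSMB recommendation to stop is needed as well.

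**The case for a change.** The strongest case for a change is that a rule for rejecting the primary null hypothesis should be reproducible from its description, and this one is not. It has three parts.

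*Recalculation.* A Lan-DeMets label usually implies recomputing bounds at the observed fraction, and the comparison uses the As Treated population. Appendix B describes its interim counts as net of loss ("n.interim1 is the expected effective sample size at the 1st interim, after 5% loss", and likewise "n.interim2 is the expected effective sample size at the 2nd interim, after 5% loss"): 31 and 77 per arm. Dividing by 324 gives 62/324 = 19.1% and 154/324 = 47.5%, which would move the bounds. But that puts post-loss counts over a pre-loss total. On the matching base of 2 x 154 = 308 they are 62/308 = 20.1% and 154/308 = 50%. The SAP prints fixed thresholds for the 20% and 50% looks and nowhere calls for recalculation.

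*Continuation.* No final value accompanies the pair. The SAP, however, describes this comparison only after a recommendation to stop, followed by discussion with FDA, and sets out no return to enrolment. Writing in the matching classical value of 1.977 would not cover that case anyway. Pooled success of 64% or less sends the sample size to 510 to 536, so the second look falls at about 0.30 to 0.32 of the information (162/536 = 0.302; 162/510 = 0.318), not 0.50. If the bounds were used without the pooled trigger, the total would be about 2.65% with a final 1.96 and about 2.56% with 1.977. Holding 2.5% would need about 1.988.

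*Attribution.* This part stands: the label does not lead to the numbers. It is not proof of an error, though. Lan-DeMets allows any non-decreasing spend. The two-sided 0.05 form gives 4.416 and 2.800 at fractions 0.197 and 0.49, which round to the printed pair; nothing suggests those fractions were used, but the attribution is sensitive to small shifts.

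**Conclusion.** No change to the plan follows. The label is loose: at the nominal looks the printed pair is the classical O'Brien-Fleming boundary, and none of the standard Lan-DeMets functions tried at the documented fractions gives both values. But the plan prints the thresholds, and an analyst need only compare Z with 4.42 or 2.80. As fixed values they spend 0.26% by the second look, and with a final stop the simulated error was 2.38% or less. Correcting the name would alter no decision. Adopting another function's bounds would move the cut-off by at most about one subject per arm, with no shown gain, on a path that is practically closed at the planned 90% success rate and has a 4.7% chance of its 50% trigger even at 70%.

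The conclusion assumes that the bounds are applied as printed and that a stop taken on this path is final, which is how SAP 4.2.1.2 reads. If the trial were ever continued after an unblinded comparison, the final critical value would have to be worked out for the sample size then in force. That would belong to the discussion with FDA that the SAP already requires.
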